5. MANAGEMENT OF DATA AND SAMPLES

a. Storage

We will follow NIH guidelines to prevent identification of study participants and other violations of subject confidentiality. Information will be stored using a confidential case number, and no identifiers (name, address, phone number, etc.) will be used that could allow direct linking of database information to individual subjects. Secure e-mail will be used for all electronic communications of subject information between

investigators. Demographic and clinical data will be archived on a password-protected server.

All diagnostic information collected from patients will be recorded in the medical record and CRIS system according to the policies of the NIH Clinical Center Medical Records Department. Research data will be stored on secure servers or in locked cabinets in a room that is kept locked when unoccupied. Blood samples will be stored in locked freezers in laboratories of protocol investigators. All specimens will be labeled with a code that does not include patient identifiers.

Protocol investigators will have access to all clinical data. Laboratory staff of the protocol investigators will have access to coded specimens. All imaging data will be stored on the NIMH server under password-protected accounts accessible only to the principal investigator and directly involved study personnel to preserve subject privacy. All data are regularly backed up, either by the NIMH system administrator or by NIMH CIT personnel.

Any loss or destruction of samples will be reported to the IRB.

Upon termination of the protocol, data will be deposited in a repository protocol to facilitate future data sharing according to the initial protocol consent. Unused samples will be destroyed.

b. Data and sample sharing plan

This protocol is not subject to the Genomic Data Sharing (GDS) policy. It does not generate “large-scale” human genomic data as defined in the NIH Supplemental Information to the GDS Policy. Image and other research data including genetic results will be shared with collaborating laboratories outside of NIH: Banner Alzheimer’s Institute (Phoenix, AZ) under FWA #00002630, Memory and Aging Center, University of California San Francisco (San Francisco, CA) under FWA #00000068, and Georgetown University (Washington, DC) under FWA #IORG0000193.

Data may be shared with collaborating laboratories at the NIH or outside of the NIH and/or submitted to NIH-designated repositories and databases if consent for sharing was obtained. Repositories receiving data from this protocol may be open-access or restricted access.

Data will be stripped of identifiers and may be coded (“de-identified”) or unlinked from an identifying code (“anonymized”). When coded data are shared, the key to the code will not be provided to collaborators, but will remain at the NIH. Data may be shared with investigators and institutions with an FWA or operating under the Declaration of Helsinki (DoH) and reported at the time of continuing review. Sharing with investigators without an FWA or not operating under the DoH will be submitted for prospective IRB approval. Submission to NIH-sponsored or supported databases and repositories will be reported at the time of the Continuing Review. Submission to non-NIH sponsored or supported databases and repositories will be submitted for prospective IRB approval.

Required approvals from the collaborating institution will be obtained and materials will be shipped in accordance with NIH and federal regulations.

6. ADDITIONAL CONSIDERATIONS

a. Research with investigational drugs or devices

[¹¹C]ER176 will be prepared as described previously under IND 122236 held by NIMH IRP. [¹¹C]PIB will be prepared under IND 108861 held by NIMH IRP. All these PET radioligands will be synthesized in recently re-established NIMH cGMP facility.

b. Gene therapy

Not applicable.

7. RISKS AND DISCOMFORTS

Risks include those associated with: a) neurological and neuropsychological examinations, b) genetic tests for rs6971 TSPO polymorphism, c) MRI, d) placement of a venous and an arterial line, e) arterial blood sampling, f) radiation exposure from [¹¹C]ER176, [¹¹C]PIB, and the transmission scan, and g) PET scanning.

a. Neurological and neuropsychological examinations

The clinical examinations and ratings may be tiring. The neuropsychological tests are not harmful, but may be frustrating or stressful. If patients do not wish to do a test, that test will not be administered.

b. Genetic test for rs6971 TSPO polymorphism

Venous blood sampling for the genetic test is associated with only minimal risk. There is usually some discomfort when the needle is inserted for phlebotomy.

The result of TSPO polymorphism will be used only for later PET data analysis, and not shared with study participants or their family. Since the clinical significance of TSPO polymorphism is unknown other than different level of binding affinity to PET radioligands, the risk would be low even if the genetic information happens to be reidentified.

c. MRI

People are at risk for injury from the MRI magnet if they have pacemakers or other implanted electrical devices, brain stimulators, some types of dental implants, aneurysm clips (metal clips on the wall of a large artery), metallic prostheses (including metal pins and rods, heart valves, and cochlear implants), permanent eyeliner, implanted delivery pump, or shrapnel fragments. Welders and metal workers are also at risk for injury because of possible small metal fragments in the eye of which they may be unaware. Subjects will be screened again for these conditions before having any scan, and if they have any, they will not receive an MRI scan.

It is not known if MRI is completely safe for a developing fetus. Therefore, all women of childbearing potential will have a urine pregnancy test performed no more than 24 hours before each MRI scan. The scan will not be done if the pregnancy test is positive.

People with fear of confined spaces may become anxious during an MRI. Those with back problems may have back pain or discomfort from lying in the scanner. The noise from the scanner is loud enough to damage hearing, especially in people who already have hearing loss. Everyone having a research MRI scan will be fitted with hearing protection. Subjects will be asked to complete an MRI screening form for each MRI scan they have. There are no known long-term risks associated with MRI scans.

d. Placement of a venous and/or an arterial line

Venous catheter insertion can be associated with discomfort, bruising, infection, or clot formation. Using proper placement techniques will minimize these risks. In case of tracer extravasation, we will stop the study, remove the venous line from the arm, and apply cold to the site.

Arterial catheterization has been shown to be a generally safe and reliable method of obtaining arterial blood samples (Lockwood, 1985). Placement of a radial arterial catheter may cause bruising or infection. There is also a risk of occlusion and microemboli. Over 3,000 arterial catheters have been placed to date in the PET Department. Of these, only two complications requiring physician's care arose. In the first case, a small radial artery aneurysm developed several months later, which was successfully repaired surgically. In the second case, a radial artery thrombosis developed 28 days later, which was also successfully repaired surgically.

e. Blood sampling

Participants may have arterial (or venous) blood sampling. The total amount of blood drawn will not exceed 400 mL. Blood sampling may lead to the formation of small subcutaneous hematomas caused by blood leaking from a punctured blood vessel. Such hematomas cause only minor discomfort. They are not dangerous and require no treatment other than reassuring the patient. There is also a small risk of infection at the site of the needle puncture, which can be readily treated with antibiotic therapy. We will ask participants not to donate blood within 8 weeks prior to the study or for 8 weeks following the study.

f. Radiation exposure risks

Radiation exposure in this protocol will be from [¹¹C]ER176, [¹¹C]PIB, and the associated transmission scans.

In our previous study with [¹¹C]ER176, we calculated the radiation exposure of the radioligand from whole-body imaging in nine healthy subjects (Ikawa *et al*, 2017). The radiation exposure (rem) from a 20 mCi injection was: effective dose (0.30), with three highest organs kidneys (1.06), spleen (1.00), and lungs (0.77).

According to a published data with [¹¹C]PIB, the radiation exposure (rem) from a 10 mCi injection is: effective dose (0.18), with three highest organs gallbladder wall (1.54), liver (0.70), and urinary bladder wall (0.61) (Scheinin *et al*, 2007).

With regard to exposure from the transmission scan, the PET Department recently implemented [name] suggestion to decrease the current (amperage) and, thereby, the radiation from the CT. We do not need a high resolution (high current) image for attenuation correction; a low resolution, like that from a line source, is perfectly adequate to correct attenuation in the PET emission scan. With the lowered current, the exposure to the lens of the eye is now 0.26 rem, about 1/3 of the previous value.

We wish to maintain flexibility in the choice of PET cameras. Among the various PET cameras, PET/CT has the highest exposure. In addition, we routinely include the dose from two transmission scans in the event that it must be repeated in a subject. The effective doses for two head transmission scan from a PET/CT are ~0.04. Thus, the total effective dose in each [¹¹C]ER176 PET scan is 0.34 rem, and each [¹¹C]PIB PET scan is 0.22 rem. Each subject will undergo one [¹¹C]ER176 and one [¹¹C]PIB PET scans and the total effective dose in six months is 0.56 rem, and may be 1.12 rem in a year if the subject is re-evaluated

within a year after the first evaluation. If a subject is fully re-evaluated following the schedule in Table 1 after one year, two years, and three to five years from the first evaluation, the total effective dose is 2.24 rem in five years, which is well below the limit of 5 rem per year established by NIH's Radiation Safety Committee. All subjects will be asked about any prior research participation involving radiation exposure so that the total exposure, in combination with the present study, will not exceed an effective dose of 5 rem per year.

g. PET scan

PET scans, which detect injected radioactivity within the body, are not associated with any known physical hazards to the subject lying on the table. We routinely use a series of procedures to minimize the risk of discomfort during scanning sessions. Namely, the procedures are conducted in the presence of trained health professionals to whom participants will have ready access should they experience any problems. Participants can communicate with the trained health professionals while in the scanner and can be removed from the scanner and withdraw from the study at any time if they wish to do so. Participants can also request that the operator stop the scan.

8. SUBJECT SAFETY MONITORING

a. Parameters to be monitored

The subjects will be evaluated by a physician upon entry into the protocol and monitored by a physician or nurse practitioner throughout their participation in the protocol, including during the PET procedure. Pulse rate, blood pressure, respiratory rate, and EKG (either 3- or 12-lead) will be recorded within three hours before tracer injection and again at about 15, 30, and 120 minutes after injection. Laboratory tests including CBC, blood chemistry, and urinalysis will be done before and after tracer administration to monitor for changes.

A credentialed, licensed independent practitioner will be present during the neurological examination. Neuropsychological testing will be carried out by trained evaluators.

Testing will be performed in the NIH Clinical Center. It is anticipated that most patients will be evaluated as outpatients, but occasionally patients may be admitted to the inpatient ward for convenience. Testing will be done in outpatient clinic areas, Neurotesting Unit, day hospital, or NMR center with trained medical personnel and emergency equipment immediately available.

Procedures may be stopped for any of the following reasons:

- 1) The patient may request to have the procedure stopped.
- 2) In the investigator's judgment, continuing the procedure would be detrimental to the patient's health and well-being.

b. Toxicity criteria

Toxicity will be assessed according to the NCI Common Terminology Criteria for Adverse Events (CTCAE) v.4.03 <http://evs.nci.nih.gov/ftp1/CTCAE/About.html>.

c. Criteria for individual subject withdrawal

A patient may be taken off the protocol for any of the following reasons:

- 1) The patient may request to withdraw from the protocol at any time they wish.
- 2) In the investigator's judgment, continued participation in the study would be detrimental to the patient's health and well-being.
- 3) The subject fails to comply with the requirements of the protocol.

- 4) The subject's performance on testing is unreliable or they cannot be validly tested, for example, if their neurological status changes in such a way as to make interpretation of the neurological cause of their impairment impossible.
- 5) The patient becomes too disabled to travel to NIH for the follow-up evaluation testing.
- 6) If a patient no longer has capacity to give consent and does not have a suitable DPA.

9. OUTCOME MEASURES

a. Primary outcome measures

Difference of [¹¹C]ER176 brain uptake between healthy controls and neurodegeneration subjects.

b. Secondary outcome measures

- 1) Disease-specific patterns of [¹¹C]ER176 TSPO brain uptake across different neurodegenerative diseases.

The clinical phenotype of individuals with neurodegenerative diseases differs based on disease subtype, which in turn reflects differences in regional neurodegeneration across disease subtypes. For example, patients with AD usually exhibit prominent degeneration in the parietal cortex and hippocampus, individuals with FTD usually exhibit degeneration in the frontal and/or temporal lobes, and individuals with ALS exhibit motor cortex degeneration. Because previous studies with 1st and 2nd generation TSPO ligands have shown anatomical correlation between areas of cortical neurodegeneration and increased TSPO ligand uptake, we anticipate that our 3rd generation TSPO ligand will reveal anatomical differences in ligand uptake across different neurodegenerative diseases. We will quantify TSPO signals in pre-selected brain regions (for example, parietal cortex, temporal cortex, frontal cortex, motor cortex) in each individual, and compare regional TSPO uptake across different brain regions as a function of disease subtype. Voxel-based morphometry analysis of cortical neurodegeneration will be used to determine if TSPO uptake correlates anatomically with regional neurodegeneration.

- 2) Longitudinal imaging of individual patients shows a correlation between interval change of tracer uptake and disease progression.

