Participants will undergo a general and neurological exam, a standard battery of neuropsychological tests to measure cognitive function, blood tests for analysis of TSPO polymorphisms, MRI of the brain, and PET imaging with the [¹¹C]ER176 TSPO radioligand and [¹¹C]PIB amyloid radioligand. Participants will be invited to return for repeat evaluations approximately 1, 2, and 3-5 years after their initial evaluation.

Outcome measures

Brain PET and MRI scans will be co-registered for anatomic definition of regions of interest, and SUV will be calculated in various brain regions. [¹¹C]ER176 PET data will be analyzed with compartmental modeling. [¹¹C]PIB PET and MRI data will be adjunctly used for segregating the collected data by disease subtype. For the primary objective, we will compare TSPO radioligand uptake of healthy controls compared to subjects with neurodegenerative diseases. For secondary objectives, we will determine if neuroanatomical regions of tracer uptake differ across different neurodegenerative disease subtypes, and if interval change of tracer uptake correlates with disease progression in longitudinal imaging of individual subjects.

Table of Contents

PRÉCIS:	3
LIST OF ABBREVIATIONS	5
1. INTRODUCTION AND BACKGROUND.	5
2. STUDY OBJECTIVES	9
3. SUBJECTS	9
4. STUDY DESIGN AND METHODS	11
5. MANAGEMENT OF DATA AND SAMPLES	17
6. ADDITIONAL CONSIDERATIONS	19
7. RISKS AND DISCOMFORTS	19
8. SUBJECT SAFETY MONITORING	21
9. OUTCOME MEASURES	22
10. STATISTICAL ANALYSIS	22
11. HUMAN SUBJECTS PROTECTION	23
12. BENEFIT	24
13. CONSENT DOCUMENTS AND PROCESS	24
14. DATA AND SAFETY MONITORING	25
15. QUALITY ASSURANCE (QA)	26
16. REPORTING OF UNANTICIPATED PROBLEMS, ADVERSE EVENTS AND PROTOCOL DEVIATIONS	26
17. ALTERNATIVES TO PARTICIPATION	27
18. PRIVACY	27
19. CONFIDENTIALITY	27
20. CONFLICT OF INTEREST	27
21. RESEARCH AND TRAVEL COMPENSATION	28
22. REFERENCES	29

LIST OF ABBREVIATIONS

AD	Alzheimer's disease
ALS	amyotrophic lateral sclerosis
C9ORF72	chromosome 9 open reading frame 72
DLB	dementia with Lewy bodies
FTD	frontotemporal dementia
GRN	progranulin gene
HAB	high-affinity binder
IL	interleukin
LAB	low-affinity binder
MAB	mixed-affinity binder
MND	motor neuron disease
MRI	magnetic resonance imaging
PBR	peripheral benzodiazepine receptor
PD	Parkinson's disease
PGRN	progranulin protein
PET	positron emission tomography
PIB	Pittsburgh compound B
SUV	standardized uptake value
TBK1	TANK-binding kinase 1
TNF	tumor necrosis factor

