2. STUDY OBJECTIVES

a. Primary objectives

We will explore if human subjects with neurodegenerative diseases exhibit different brain uptake levels of the [^{11}C]ER176 TSPO ligand compared to control subjects.

b. Secondary objectives

We will explore if,

- 1) [^{11}C]ER176 TSPO brain uptake shows disease-specific patterns across different neurodegenerative diseases
- 2) Longitudinal imaging of individual patients shows that interval changes in tracer uptake correlate with disease progression.

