10. STATISTICAL ANALYSIS

a. Analysis of data/ study outcomes

PET and MRI scans will be coregistered for anatomic definition of regions of interest. SUV will be calculated in various brain regions. Parametric images will be created using PMOD software (PMOD Technologies Ltd., Zurich, Switzerland). Brain imaging data and/or blood data will be analyzed with compartmental modeling to achieve quantitation of each radioligand's target binding (e.g. V_T , V_T/f_P , SUV ratio) using PMOD software. Cross-sectional or longitudinal group comparison and correlation analysis with other clinical parameters will be conducted in each brain region using either regions-of-interest or voxel-based image analysis method. Statistical analyses will include ANCOVA for cross-sectional comparison among groups, and multilevel mixed model for longitudinal comparison among groups.

b. Power analysis

This study is exploratory and we do not know how much would [¹¹C]ER176 brain uptake be different between dementia patients and healthy subjects. Thus, a formal power calculation is impossible. We request accrual ceiling of 100 subjects with a diagnosis or with an increased risk of an age-related neurodegenerative diseases and 100 age and sex-matched healthy volunteers. Dropouts will not be replaced.

With regard to the interim analysis in cross-sectional part of this study, we plan to collect approximately 10-15 subjects in each of two groups: healthy controls and patients with neurodegenerative diseases. In our previous data from five FTD patients and control subjects scanned with [¹¹C]PBR28, which is an older generation TSPO radioligand, the estimated effect size was 0.50-0.65 in ANCOVA with TSPO genotype and demographic factors as covariates at a significance level of 0.05. If we assume [¹¹C]ER176 has the same effect size and variability with [¹¹C]PBR28, 10-15 subjects in two groups could achieve 79-93% power in the same statistical condition by G*Power program (v 3.0, University of Düsseldorf, Germany).

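### The stated 79–93% interim power uses only the top of its own effect-size range and rests on an FTD-only pilot, while the contrast pools diseases with no primary region fixed

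*Combined protocol and SAP*

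**What the plan says.** The primary objective (section 2.a) opens: "We will explore if human subjects with neurodegenerative diseases exhibit different brain uptake levels of the" tracer in question. The Précis adds: "For the primary objective, we will compare TSPO radioligand uptake of healthy controls compared to subjects with neurodegenerative diseases". Section 9.a repeats this as a difference in "brain uptake between healthy controls and neurodegeneration subjects". None of the three names a region, a composite or an uptake measure.

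Section 9.b, under a secondary outcome, says of AD and FTD that "patients with AD usually exhibit prominent degeneration in the parietal cortex and hippocampus, individuals with FTD usually exhibit degeneration in the frontal" (for FTD it names the temporal lobe as a further or alternative site). Of ALS it says that "individuals with ALS exhibit motor cortex degeneration". On the analysis it says: "We will quantify TSPO signals in pre-selected brain regions (for example, parietal cortex, temporal cortex, frontal cortex, motor cortex) in each individual". The regions are given as examples and serve the disease-pattern outcome, not the primary one.

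Section 10.a leaves region and method open: "Cross-sectional or longitudinal group comparison and correlation analysis with other clinical parameters will be conducted in each brain region using either regions-of-interest or voxel-based". On the measure it says: "Brain imaging data and/or blood data will be analyzed with compartmental modeling to achieve quantitation of each". That sentence concerns tracer binding and gives V_T, V_T/f_P and SUV ratio as examples; SUV is also calculated.

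Section 10.b calls the study exploratory and a formal power calculation impossible. For the interim it assumes that ER176 has the same effect size and variability as the older tracer PBR28, takes 0.50–0.65 from five FTD patients and controls (ANCOVA, level 0.05), and reports 79–93% power for 10–15 subjects per group. Section 4.a uses this interim to judge whether uptake differs significantly between patients and controls and, if necessary, to modify further data collection. Sections 4.a and 4.d allow ER176 scans with venous sampling or no blood sampling, and describe a substitute analysis still to be developed.

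**The concern.** The power statement is the only quantitative support for the cross-sectional comparison, and the interim may change later data collection. A non-significant result would naturally be read against a stated 79–93%. That reading fails on two counts.

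First, the stated range does not appear to cover the effect-size range it is attached to. Second, the effect comes from one disease, but the interim patient group may contain any of the eligible diagnoses. The assumption in section 10.b bridges the change of tracer only; it is silent on the change of disease mix. By section 9.b's own account, a region suited to FTD need not be the one affected in AD or ALS. With no primary region or composite fixed, the contrast to which the power applies is undefined.

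A smaller gap concerns the measure. V_T and V_T/f_P require blood data. Some scans will lack arterial data, and nothing says whether they are omitted, substituted or analysed on another scale in the primary contrast.

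**Working it through.** **Inputs.** Effect size 0.50–0.65, level 0.05, 10–15 per group, stated power 79–93% (section 10.b). Pilot: 5 FTD patients and 13 controls; p = 0.034 in prefrontal cortex and 0.025 in striatum; V_T/f_P adjusted for age, sex, education and TSPO genotype (section 1). Assumptions: the effect size is Cohen's f, and genotype takes one degree of freedom, giving four covariates.

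**1. Reproducing the stated figure.** Two-group ANCOVA: noncentral F with 1 and N − 2 − c degrees of freedom (c covariates) and noncentrality λ = f²N.

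| f | N (per group) | λ | Power, c = 0 | Power, c = 4 |
|---|---|---|---|---|
| 0.65 | 20 (10) | 0.4225 × 20 = 8.45 | 78.5% | 77.1% |
| 0.65 | 30 (15) | 0.4225 × 30 = 12.68 | 93.0% | 92.7% |
| 0.50 | 20 (10) | 0.25 × 20 = 5.00 | 56.2% | 54.8% |
| 0.50 | 30 (15) | 0.25 × 30 = 7.50 | 75.3% | 74.8% |

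Both stated endpoints match f = 0.65, at 10 and 15 per group. The lower effect size does not enter them. Over the plan's own range, power is about 55–79% at 10 per group and 75–93% at 15.

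Other readings of the effect size fail. Cohen's d of 0.50–0.65 gives 20–43% two-sided; partial eta-squared of 0.50–0.65 gives 99–100%.

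**2. Is the effect size that of the section 1 pilot?** With 18 − 2 − 4 = 12 residual degrees of freedom, p = 0.034 gives F = 5.72 and p = 0.025 gives F = 6.55. Then √(F/18) is 0.56 and 0.60, inside 0.50–0.65. The alternative √(F/12) gives 0.69 and 0.74, outside it. The match is plausible but not proven. That the source is FTD-only needs no inference, because section 10.b says so.

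**3. Effect of pooling (illustration).** The documents give no disease mix. Let a share π of patients have the full shift d = 2f in the tested region, and the rest a fraction h of it. In units of the within-group SD, the mean shift is d[π + h(1 − π)] and the pooled variance is 1 + ½π(1 − π)(1 − h)²d². The effective f is half the mean shift divided by the square root of that variance. Power uses c = 4.

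No effect elsewhere (h = 0):

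| π | f | Effective f | 10 per group | 15 per group |
|---|---|---|---|---|
| 1/2 | 0.50 | 0.25/√1.125 = 0.236 | 17% | 24% |
| 1/2 | 0.65 | 0.325/√1.211 = 0.295 | 23% | 34% |
| 2/3 | 0.50 | 0.333/√1.111 = 0.316 | 26% | 38% |
| 2/3 | 0.65 | 0.433/√1.188 = 0.398 | 38% | 55% |

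Half-size effect elsewhere (h = ½):

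| π | f | Effective f | 10 per group | 15 per group |
|---|---|---|---|---|
| 1/2 | 0.50 | 0.375/√1.031 = 0.369 | 34% | 49% |
| 1/2 | 0.65 | 0.4875/√1.053 = 0.475 | 51% | 70% |
| 2/3 | 0.50 | 0.417/√1.028 = 0.411 | 40% | 58% |
| 2/3 | 0.65 | 0.542/√1.047 = 0.529 | 60% | 79% |

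Every entry is below the unpooled power for the same f and sample size, but the size of the loss depends heavily on h and π.

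**4. Scans without arterial data.** No arithmetic applies, because no rate is given. Section 4.a words the exception for patients, and section 3.b requires only healthy subjects to be willing and able to complete all procedures. Section 4.d, however, speaks of subjects generally, allows other reasons, and makes the line a consent-form option. Absence may be more common in patients, but this is not stated.

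**The case against.** The study calls itself exploratory, the interim power is explicitly conditional, and the interim serves planning with no stopping rule. That stands: nothing here shows that an early efficacy claim is planned or that an error rate was promised and broken, so no multiplicity adjustment is needed. It does not rescue a stated range that omits the lower half of its own input, or its use for a different patient group.

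The measure is less open than section 10.a alone suggests. The Précis says ER176 data will be analysed by compartmental modelling, section 1 presents V_T as this tracer's strength, and SUV ratio may be listed for PIB, which has no arterial sampling. This largely stands. What remains open is V_T versus V_T/f_P and the handling of scans without arterial data.

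Disease effects may overlap between regions: the pilot found increases in striatum as well as prefrontal cortex, and section 9.b says usually, not always. This also stands. A reader might infer that interim power collapses almost to the test level. That needs a small affected share and no effect at all elsewhere, which the documents do not establish.

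A reader might also infer that arterial data will be missing mainly in patients and will bias the difference toward zero. The texts compared in step 4 do not support a rate or a direction, and refusal of a line need not reflect severity.

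**Conclusion.** The point holds on power and on the undefined primary contrast. If 0.50–0.65 is Cohen's f, the interim power over the plan's own inputs is about 55–93%, not 79–93%. This is also the power for an FTD-like group in an affected region, not for the pooled group. The illustrated 17–55% (half to two thirds of patients affected, none elsewhere) shows how far it could fall; a half-size effect elsewhere gives 34–79%. Neither range is a forecast, since the disease mix and effects outside each disease's typical regions are unknown.

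That the effect size came from V_T/f_P in prefrontal cortex or striatum is likely but inferred, and should not be entered in the protocol as fact without the sponsor's confirmation. The missing rule for non-arterial scans is a lesser gap in detail. No claim is made about power at the accrual ceiling. The change should be made before the interim.

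**What to change.** 1. **Section 10.b.** Restate the interim power over the full effect-size range (about 55–79% at 10 per group, 75–93% at 15). Say that it rests on an FTD-only pilot and is not the power for a pooled disease group, or recompute it for the contrast chosen.
2. **Sections 9.a and 10.a, before the interim.** Fix one primary region set or composite suited to the mixed group. One option is a set per diagnosis, with controls measured in the same regions and values standardised by region. The other is a common composite with the dilution acknowledged. Label other region and voxel results exploratory.
3. **Section 10.a.** Name V_T or V_T/f_P as the primary ER176 measure, consistent with the Précis. Keep scans without arterial data out of that contrast until the substitute method has been checked against arterial values. Report their numbers by group, and add a supporting SUV analysis of all participants.

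The cost is wording, with no added scans, visits or participants. A per-diagnosis set needs a diagnosis-to-region table that also covers eligible diagnoses section 9.b does not mention, such as Huntington disease and corticobasal syndrome, and says where at-risk subjects belong. An arterial-based primary measure loses the participants scanned without arterial data.
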